For pregnant women, a risk scoring tool has also been developed to help identify those at greater HIV risk (20). This tool, developed and validated using data from 1,304 women living in Kenya, includes the following variables: Partner HIV status unknown, number of lifetime sexual partners, and history of syphilis. Women with a score >6 made up 16% of the population but accounted for 56% of HIV acquisition events.

For pregnant women, risk assessment alone may not identify all women at risk of HIV acquisition during pregnancy. Partner self-testing is a strategy that has been successfully used to identify previously unknown HIV-positive partners of pregnant women in Western Kenya. A recent study demonstrated high uptake of partner-testing when multiple self-tests are given distributed to women in antenatal care clinics along with instructions about how to use the tests and counseling about using discretion when determining whether to offer a self-test to sexual partners (21). Of women enrolled in the study, 91% (of 58 participants) reported distributing the self-test to their primary sexual partner *and* being present when their partner used the test (21). The strategy was also found safe for women who participated. This study did exclude a small number of women attending clinics who believed violence could occur from distributing the self-tests, who would likely benefit from PrEP given the risk of violence in their relationship. Including a self-testing intervention that increases partner self-testing will allow this study to identify women who may be categorized as low risk in the risk assessment but have a previously unknown HIV positive partner.

Pre-Exposure Prophylaxis (PrEP) and Women

[figure not shown]
As new studies examine topical microbicides and long-acting PrEP formulations for HIV prevention (22-25), oral PrEP remains a leading candidate for pregnancy given substantial evidence of efficacy, safety, and lack of potential for genital tract irritation that could precipitate preterm birth or ascending infection in pregnancy (26). Increasing partner ART use is another highly effective and complementary approach (27). Condoms, though effective, have not been widely adopted by pregnant/postpartum women, who are usually married and find it difficult to negotiate for condom use in the setting of a presumably stable relationship.

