Following routine antenatal HIV testing during an antenatal care (ANC) visit, the study nurse will recruit HIV seronegative women and determine eligibility. Following screening consent, a brief screening form will capture age, gestational age, and eligibility characteristics. For women identified as eligible for the study, we will obtain written informed consent for participation and the women will be enrolled. The informed consent will emphasize that participation in this study is completely voluntary and will not affect their ability to receive antenatal, delivery or postnatal care at this or any other facility. This study will utilize two versions of the consent form, one used in universal PrEP counseling facilities and one used in targeted PrEP counseling facilities to explicitly describe the facility-specific procedures participants will undergo. A screening & enrollment log will capture the proportion of women screened, deemed to be eligible, and eventually enrolled, to determine the ratios of clinic attendees:screened and eligible:enrolled, which will aid in estimates of generalizability. We will also collect data from each facility on the total number of ANC attendees per month.

e) STUDY PROCEDURES

Enrollment data collection:

Enrollment for all study participants will include a detailed questionnaire, including assessment of demographics, mental health, social support systems, drug and alcohol use, risk perception, risk score, partner HIV status, education, prior obstetric history, education, marital status and income. Data from the MCH card will be abstracted, including confirmation of HIV results as well as results

of antenatal syphilis testing. As is standard of care in MCH clinics, in both trial arms a referral letter encouraging HIV testing will be provided for women to give to partners and clinic-based HIV testing will be available for any male partner seeking testing.

Universal PrEP Clinics, Enrollment Visit (N=10):

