### **Randomization scheme text for a randomized, unblinded study**

The facility-level cluster randomization will be conducted using a restricted randomization approach based on new antenatal care clinic (ANC) volume, and county. County will be used as a proxy for HIV prevalence.

We will select 20 clinics from Western Kenya. Ten clinics will be randomized to universal PrEP and ten to targeted PrEP (Table 2). To ensure balance between study arms in terms of key site characteristics, sites will be categorized on HIV prevalence and ANC volume, and restricted randomization will be used for site (cluster) allocation to intervention and control arms (67). Specifically, all possible randomizations that evenly distribute sites on these two specified factors (HIV prevalence, ANC volume) into 2 study arms will be generated, and one combination will be selected using a random number generator. Randomization and allocation will be performed by [name], who has no knowledge of sites other than the variables included in the restricted randomization process.

In order to build excitement for the study among study staff and facility representatives, we aim to conduct the final randomization activities as part of the study training. Prior to the training, each facility was ranked by county and ANC volume and assigned to one of six groups. The ANC volume and county for each group are summarized in Table 1.

Table 1: Summary of facility group assignments for PrIMA randomization activities			
Group	County	Number of Facilities	Mean ANC Volume (SD)
1	Homa Bay	2	173 (60.8)
2	Homa Bay	4	59.8 (1.3)
3	Homa Bay	4	53.8 (3.3)
4	Siaya	2	140 (26.9)
5	Siaya	4	54.8 (6.4)
6	Siaya	4	38 (5.5)

One representative from each facility will be identified to represent their facility during the randomization event. Representatives from facilities in each group will be asked to select a ball from a bag during the PrIMA training. The bag will contain one ball per facility, and half of the balls will be blue (universal arm) and half of the balls will be orange (targeted arm). The final facility randomization will be determined by what color ping pong ball the facility representative selects. Facility group assignments are including in Table 2.

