**Supplementary Table 1. Distribution of demographic characteristics of women screened and enrolled in the study**

	N (%) or Median (IQR)			
	Project arm			
	Universal		Targeted	
	Screened (n=)	Enrolled (n=)	Screened (n=)	Enrolled (n=)
Demographic characteristics				
Age (years)				
Median				
<10				
21-34				
≥35				
Gestational age (weeks)				
Plan to receive postnatal care services at this facility				

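### Women are recruited after their clinic's arm is openly known, but the plan records no risk items on eligible women who do not enrol and pre-specifies no risk-adjusted analysis

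*Protocol*

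**What the plan says.** **Allocation.** The SAP section headed "Randomization scheme text for a randomized, unblinded study" has facility representatives draw coloured balls, and says "we aim to conduct the final randomization activities as part of the study training". Arms are therefore openly known when recruitment starts.

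**Recruitment.** Protocol Component 1, d) says that after routine antenatal HIV testing "the study nurse will recruit HIV seronegative women and determine eligibility". Written consent then uses one of two arm-specific forms: "This study will utilize two versions of the consent form, one used in universal PrEP counseling facilities and one used in targeted" facilities.

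**Screening data.** In the same section, "a brief screening form will capture age, gestational age, and eligibility characteristics". The itemised list in Component 1, g) Data collection instruments gives age, gestational age, HIV status and plans to stay in the area. A log will be kept "to determine the ratios of clinic attendees:screened and eligible:enrolled, which will aid in estimates of generalizability".

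**Enrolment data.** Component 1, e) collects the risk score and partner HIV status from all participants in both arms, and takes syphilis results from the MCH card. SAP shell Table 1 tabulates lifetime partners, partner HIV status and RPR by arm.

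**Screened versus enrolled.** SAP Supplementary Table 1, "Distribution of demographic characteristics of women screened and enrolled in the study", is split by arm but holds only age, gestational age and the plan to receive postnatal care at the facility.

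**Analysis.** SAP section 4 says only that the primary analyses are intention-to-treat. Section 5 gives GEE comparisons by arm for PrEP exposure and other outcomes. It names no covariates, and it gives no method for HIV incidence.

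**The concern.** Restricted randomisation balances clinics on county and antenatal volume. It does not govern which women within a clinic are approached and agree. When recruiter and woman both know the arm, and the consent form describes that arm's procedures, the women who enrol can differ between arms.

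The primary comparison is HIV incidence among all enrolled women, so a difference in baseline risk between arms feeds directly into the incidence ratio. It also affects PrEP exposure, and appropriate PrEP use, which is defined by risk status.

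The protocol's literature review shows that the issue is not fanciful. Of the cited self-testing study it says "This study did exclude a small number of women attending clinics who believed violence could occur from distributing the self-tests", and adds that such women would probably benefit from PrEP. That exclusion belongs to the cited study, not to this trial, but it shows that willingness to take part in partner self-testing can be related to risk.

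**Working it through.** **1. The plan's own sample size.** The plan states 10 clinics per arm of 200 women, 4% vs 2%, k = 0.2, 80% power. Two-sided alpha of 0.05 is assumed because the text does not state it. The cluster formula for proportions is c = a + (1.96 + 0.84)² × V / (p0 − p1)², with V = p0(1−p0)/n + p1(1−p1)/n + k²(p0² + p1²).

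- V = 0.04×0.96/200 + 0.02×0.98/200 + 0.04×(0.0016 + 0.0004) = 0.00037.
- c = a + 7.849 × 0.00037/0.0004 = a + 7.26.
- With a = 2 this is 9.26, so 10 clinics. The same form reproduces all seven rows of the table. With a = 1 (unmatched) each row needs one clinic fewer.

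The stated figure is reproduced. It makes no allowance for a difference in risk mix between arms.

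**2. Strength of the risk score.** Protocol 7a) Literature review: women scoring above 6 were 16% of the cohort and had 56% of infections. High:low incidence ratio = (0.56/0.16)/(0.44/0.84) = 3.50/0.524 = 6.68.

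**3. Spurious incidence ratio with no true effect.** If a share h of an arm is high-risk, its incidence is proportional to 1 + 5.68h. The shares below are assumptions. The documents supply only the 16% base.

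| Universal | Targeted | Calculation | Ratio, targeted/universal |
|---|---|---|---|
| 16% | 14% | 1.795/1.909 | 0.94 |
| 16% | 12% | 1.682/1.909 | 0.88 |
| 16% | 10% | 1.568/1.909 | 0.82 |
| 20% | 14% | 1.795/2.136 | 0.84 |
| 12% | 16% | 1.909/1.682 | 1.14 |
| 16% | 0% | 1/1.909 | 0.52 |

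The 12% vs 16% row shows the reverse direction. The last row shows that score mix alone cannot produce the design ratio of 0.50. PrEP use among high scorers would lower the 6.68, so these are upper-end biases.

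**4. Effect on the test.** Take 4% in universal clinics, no true effect, and a spurious ratio of 0.88, so 3.52% in targeted clinics.

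- V = 0.000192 + 0.000170 + 0.04×(0.0016 + 0.00124) = 0.000475.
- With c − 1 = 9, z = √(9 × 0.0048²/0.000475) = 0.66.
- The chance of a significant result favouring targeted is Φ(0.66 − 1.96), about 10%, against a nominal 2.5% in that direction. At a ratio of 0.84 it is about 14%.

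**5. Would the planned baseline table show the imbalance?** The same V applies to the high-risk share among enrolled women, with 10 clinics of 200 per arm and c − 1 = 9. The k of that share is not given, so a range is shown.

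| Shares | k = 0.1 | k = 0.2 | k = 0.3 |
|---|---|---|---|
| 16% vs 14% | 30% | 19% | 13% |
| 16% vs 12% | 85% | 62% | 41% |
| 16% vs 10% | >99% | 95% | 78% |
| 20% vs 14% | 98% | 83% | 59% |

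Example, 16% vs 12%, k = 0.2: V = 0.000672 + 0.000528 + 0.0016 = 0.0028, √(9 × 0.0016/0.0028) = 2.27, and Φ(2.27 − 1.96) = 62%.

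**6. What the tables can separate.** Shell Table 1 describes enrolled women only. An imbalance there could come from selective enrolment, chance allocation of 20 clinics, or real differences in clinic populations. Only the same items on eligible women who did not enrol would separate the first from the others, and Supplementary Table 1 does not hold them.

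**The case against.** The strongest reply is that the trial already holds the data it needs. Risk score, partner HIV status and syphilis are collected on every enrolled woman in both arms and tabulated by arm, and the log gives eligible:enrolled ratios. A reader might infer from open recruitment that the trial could neither detect nor correct an imbalance. The documents do not support that. Step 5 shows that large imbalances would usually be seen, and the same items can serve as covariates.

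A reader might also infer that the bias favours targeted PrEP. That is not established. The consent forms are not available to this review, so their deterrent or attractive content cannot be asserted. Taking a self-test kit is not a condition of enrolment: women who decline or fear violence stay in the study without one. Kits could also attract women whose partner's status is unknown, the 6-point item in the protocol's Table 5, which would bias against the hypothesis. Women with low scores in targeted clinics can still ask for PrEP.

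Nor do the documents say that nurses hand-pick women. They are simply silent on the order of approach. Room for selection probably varies. If the SAP's mean ANC volumes are monthly, which it does not state, and 15-20% of attendees are HIV-positive, then 20 enrolments a month is 20/(173 × 0.85 to 0.80) = 14% of HIV-negative attendees in the largest-volume group (2 clinics). In the four groups that hold 16 clinics (means 38 to 59.8) it is 39-66%.

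Three things survive these replies. Data that could support adjustment are not a pre-specified adjustment, and a choice made after the results of an unblinded trial are known carries less weight. Moderate imbalance could pass unnoticed. The items are partly self-reported after arm-specific consent, so reporting may differ by arm and unmeasured risk stays uncorrected.

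**Conclusion.** The point holds as a gap in recording and pre-specification. Recruitment after open allocation with arm-specific consent leaves room for differential enrolment by HIV risk, in either direction. The planned data would usually reveal a sizeable imbalance in measured risk but could not explain it, and the SAP does not say what the analysis would do about it.

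The size is illustrative: incidence ratios of about 0.84 to 0.94 with no true effect for a deficit of 2 to 4 percentage points from 16%, or 20% vs 14%, and the mirror image for an excess. This rests on the cited cohort's 6.7-fold gradient, on assumed shares, and on no dilution by PrEP use. It is not evidence that bias will occur, and score mix alone could not create the twofold difference the trial is powered for. The change is worth making because it costs little and cannot be made as credibly once results are known.

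**What to change.** 1. **SAP section 5.** Pre-specify a supporting analysis of HIV incidence and of PrEP exposure, adjusted for the enrolment items already collected: lifetime partners, partner HIV status (positive, negative, unknown, no partner) and syphilis. Show it beside the unadjusted intention-to-treat result. Use the items rather than the total score, because the protocol's Table 5 gives a known HIV-positive partner 0 points. The HIV-incidence model must be stated first, since the SAP gives none.
2. **Screening form.** Record the three items in both arms, under the screening consent and before the arm-specific consent.
3. **Supplementary Table 1.** Add these items for screened, eligible-not-enrolled and enrolled women, by arm, with eligible:enrolled ratios by arm.
4. **Reconcile** the protocol's Table 2, which marks data on partner HIV status for the targeted arm only, with the enrolment text, which collects it from all participants. The adjustment needs it in both arms.

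**Cost.** One SAP paragraph, some table rows, and a few minutes per screened woman, including those who then decline. Asking decliners about lifetime partners and syphilis may need a small change to the screening consent. If the items cannot be added at screening, item 1 still stands and needs no new data.

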Women have persistent risk of acquiring HIV in pregnancy and postpartum and often do not perceive themselves to be at risk (1). In a meta-analysis of 19 studies including 22,803 person-years, HIV incidence in pregnant/postpartum women was 3.8 per 100 p-years, 4.7/100 p-years in pregnancy and 2.9/100 p-years postpartum (Figure 1) (2). These HIV incidence estimates are particularly high given that incidence estimation was among all women (not limited to those with seropositive partners) and appreciable HIV infection occurred despite decreased sexual activity

[figure not shown]

Figure 1: HIV Incidence in pregnancy (2)

Pregnancy and the postpartum period are characterized by dramatic hormonal and immunologic changes, changes in genital mucosa, and epithelial disruption during delivery

with decreased mucosal integrity postpartum (3-6). At the same time, sexual practices change markedly in this period. Sexual activity declines late in pregnancy and early postpartum, and male partners may seek other partners, and bring HIV back to the relationship (7-9). HIV acquisition in pregnancy/postpartum most often occurs among women who are unaware of their partner's HIV status. In Zimbabwe, among 1230 pregnant women, 239 (19%) reported their partner had been HIV tested, of whom 213 knew partner results, and 8 reported a HIV positive partner (0.6% of overall cohort). Only 1 of 14 incident HIV infections in this cohort occurred in a woman in a known serodiscordant partnership (10). Similarly, in a Kenyan cohort of 1310 pregnant women, only 1% reported knowing their partner was HIV positive, and these women had *lower* risk of HIV infection than women with unknown or reportedly HIV negative partners (11). HIV risk may be lower among the select few women who report knowing their partner's HIV-seropositive status because these partners are already on ART or use condoms. Many women do not know their partner's HIV status or believe their partner is HIV negative (12).

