Counseling at universal sites, will use a standardized counseling script to state that PrEP is available for women at risk for HIV, explain that HIV prevalence in the region is high, and will note that women with HIV positive partners or who don't know their partner's status may be at risk. Counseling will specify that women may have their own reasons to feel at risk or to want PrEP. Following standardized counseling, women will select PrEP at the same visit or will be allowed to deliberate on the decision and come back at the next visit with a decision. Women will be informed that it is advisable to use PrEP if they know their partner is HIV positive or if they do not know their partner's status and will be encouraged to bring untested partners to clinic if status is unknown. Women who select PrEP will be welcome to involve their partners in counseling regarding PrEP and those with recently diagnosed HIV positive male partners (via the clinic referral system) will be linked to care following the facilities standard linkage to care procedures.

Table 5: Risk Score Card for HIV acquisition in pregnancy

Risk factor	Value per factor	Score
No. of lifetime sexual partner		
1 point per sexual partner	Enter at least 1	
Male partner HIV status		
Male partner HIV status known or no male partner	0	
Male partner HIV status unknown	6	
Syphilis		
nonreactive	0	
reactive	5	
Total risk score		

Targeted PrEP Clinics, Enrollment Visit (N=10):

Following informed consent and enrollment data collection, the targeted PrEP clinics will provide two inter-related innovations: risk assessment-informed PrEP counselling and partner HIV Self-Test counselling.

Risk Assessment and PrEP Counselling:

The results of the PrEP risk assessment will be used to guide PrEP counselling and the offer of proceeding to the PrEP card-based eligibility assessment. Participants who score greater than 6 on the risk assessment will receive additional PrEP counselling that includes information about specific risk factors tailored to the participant (Table 5). These participants will then elect whether to proceed to the PrEP card eligibility assessment. Women

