who score 6 or less will not be individually counseled about PrEP. However, if they ask for PrEP they will enter the clinical assessment pathway and can be prescribed PrEP if found to be clinically eligible. We anticipate that participants with known HIV-positive partners will self-select for the PrEP eligibility assessment. Women who request PrEP despite not meeting the targeted PrEP criteria will be identified and approached for in-depth interviews to better understand their choices in Component 2 of the study.

Partner HIV Self-Testing:

Women will be offered HIV self-test kits to take to their partner for HIV testing. This will be used to provide further information on partner HIV-status: either initiate women in previously unidentified serodiscordant couples on PrEP at subsequent study visits, or to discontinue PrEP

for women who are able to confirm their partner's HIV-negative status. All women will be offered two self-tests so that they can take the test at the same time as their partner, if they chose to do so. If a woman does not receive the self-test counseling during the first study visit, they will receive self-testing counseling during their next study visit.

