 - Demographic information (education, obstetric history, marital status, income)
 - Risk Perception Assessment
 - Risk Score Card
 - Partner HIV status
 - Self-Efficacy
 - Social Support and Mental Health
 - IPV assessment
 - Partner Characteristic
 - PrEP attitudes and acceptability (HIV/PrEP Stigma Assessment)
- ANC Card Abstraction form
 - HIV status
 - Gestational Age
 - Maternal Age
 - Syphilis
 - TB status
- PrEP Counseling Outcomes form
- Partner self-test results
- MCH Card Abstraction Form, including:
 - Infant length
 - Birth weight
 - Gestational age at birth
 - Serial growth
 - Stillbirth
 - Neonatal mortality
 - Miscarriage
 - Infant congenital abnormality
- Infant, neonatal and maternal mortality (including WHO verbal autopsy instrument)
- Maternal follow up
 - HIV-status 6-weeks postpartum
 - 14 weeks postpartum
 - 6-months postpartum
 - HIV-status 9 months postpartum
 - Hepatitis B Antigen test result
 - Creatinine level test result
 - Sexual activity and contraceptive use
- PrEP Adherence
 - Pill Count data

- Self-Assessment
- DBS collection methods
- Discontinuation Documentation
- Health Economic Evaluation
 - Incremental costs at facility level, including costs incurred and averted
 - Costs incurred at participant level interview form
 - Time and motion data collection form

h) VARIABLES: Outcomes, indicators, and source documents

Table 7: Variables: Outcomes, Indicators, and source documents		
	Indicator	Source
Primary Outcomes		
Maternal HIV, 6-weeks pp	HIV Rapid Test	Study Visit, maternal specimens
Maternal HIV, 9-months pp	HIV Rapid Test	Study Visit, maternal specimens
PrEP Exposure	Number received PrEP/All Participants	PrEP Counseling outcome form
Secondary Outcomes		
Appropriate PrEP Use	Scored 1 for high risk women using PrEP and low risk women not using PrEP; 0 for high risk women NOT on PrEP and low risk women using PrEP	PrEP Counseling outcome form
PrEP Adherence	TFV/DP and FTC test results from 440 randomly selected specimens	Dried Blood Spots
PrEP Duration	Number of days on PrEP	Self-report captured on adherence counseling form; pharmacy records
Partners HIV Self-test	Partners Self-test result	self-report
Infant Birth weight	Birth weight	MCH card
Preterm Birth	Estimated gestational age at birth	MCH card
Infant Growth	Infant height, weight, and age for WAZ, HAZ, and WHZ Z-scores	MCH card
Cost Effectiveness Analysis Outcomes		

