## **2. STUDY ENDPOINTS**

### **Primary Outcome:**

HIV infection - a new positive HIV ELISA test after a documented negative HIV test (HIV tests will be the tests recommended and used by Kenya MOH during the course of the study)

Appropriately on PrEP –

- a. Initiated (swallowed) PrEP and meeting the risk criterion cutoff
- b. Did not initiate PrEP and low risk

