**Table 2. Primary and secondary endpoints**

	N (%) or incidence/100 py			RR (95% CI), p-value
	All subjects	Trial arm		
		Universal	Targeted	
Primary outcomes				
HIV incidence				
Initiated on PrEP				
Secondary endpoints				
'Appropriately' on PrEP (based on risk score)				
Partner known HIV status by end of follow-up				
Partner on ART if HIV infected				
TFV-DP levels (median on random sample)				

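### The 'appropriately on PrEP' outcome classifies most women with a known HIV-positive partner as low risk, so the PrEP use the protocol advises for them scores as inappropriate

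*Protocol*

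**What the plan says.** SAP section 2 counts a woman as appropriately on PrEP if she meets "Initiated (swallowed) PrEP and meeting the risk criterion cutoff", or if she did not initiate and is low risk. Protocol Table 7 (Component 1, section h) uses the same two-way scoring, with "0 for high risk women NOT on PrEP and low risk women using PrEP". SAP shell Table 2 names the basis of the classification (row label: "on PrEP (based on risk score"). SAP section 2 lists the outcome as primary; shell Table 2 and Protocol Table 7 list it as secondary.

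The SAP gives no number for the cutoff. The only trial score is Protocol Table 5 (Component 1, section e), and the only cutoff is a score above 6. Table 5 adds:

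- 1 point per lifetime sexual partner, with a minimum of 1;
- 6 points if the partner's HIV status is unknown, and 0 for "Male partner HIV status known or no male partner";
- 5 points for reactive syphilis.

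The same section treats women with a positive partner as candidates for PrEP. The universal script tells women that "it is advisable to use PrEP if they know their partner is HIV positive". The targeted-arm text says "We anticipate that participants with known HIV-positive partners will self-select for the PrEP eligibility assessment", and it uses partner self-tests to start PrEP in newly identified serodiscordant couples.

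Neither document names the visit at which risk is classified for this outcome. The risk score and partner status are collected from everyone at enrolment. Risk data may also be collected at later visits.

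**The concern.** The score and the outcome do different jobs. Table 5 predicts acquisition, and in it an unknown partner status is the risk factor. The outcome asks whether PrEP went to the women who should have it. When the score is used unaltered, a woman who knows her partner is HIV positive usually counts as someone who should not be on PrEP. Taking it as advised is scored as a failure, and going without is scored as a success.

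Self-testing can extend the problem. If risk is updated after the self-test, a partner who moves from unknown to positive lowers the woman's score by 6. A woman started on PrEP because of that result can then be scored 0.

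The outcome is the direct test of the Aim 1b hypothesis that targeting gives more appropriate use. Counselling of the affected women also differs by arm. The universal script advises PrEP, while targeted-arm women "who score 6 or less will not be individually counseled about PrEP", although they may ask for it. If uptake among women with positive partners were lower in the targeted arm, the coding would credit that arm for the women it missed.

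**Working it through.** **Step 1. Who falls at or below the cutoff.** Score = lifetime partners (at least 1) + 6 if partner status is unknown + 5 if syphilis is reactive. High risk is a score above 6.

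- Known partner status, syphilis nonreactive: the score is the number of lifetime partners, so high risk needs at least 7.
- Known partner status, syphilis reactive: 5 + number of partners, so high risk needs at least 2.
- Unknown partner status: at least 6 + 1 = 7, so always high risk.

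**Step 2. What share of women with a known positive partner this covers.** The documents give no distribution of lifetime partners for this population, so I varied it. Let a be the proportion with at least 7 partners, b the proportion with at least 2, and s the proportion with reactive syphilis. The share coded low risk is 1 − [(1 − s)a + s·b].

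- With a = 2% to 20%, s = 1% to 10% and b = 80% to 100% (all assumed), 72% to 97% are coded low risk. At a = 40% it is still 54% to 60%.
- With lifetime partners taken as 1 + Poisson and s = 1% to 5%, the share is 97% to 99% at a mean of 2, 87% to 91% at 4, 59% to 61% at 6 and 42% to 44% at 7. Among the means tried (2 to 7), it drops below half only at 7.

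**Step 3. How many women, at enrolment.** Protocol section 7 (HIV Acquisition in Pregnancy and Postpartum) describes one cohort in which 8 of 1230 women reported a positive partner, and a Kenyan cohort in which "only 1% reported knowing their partner was HIV positive".

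- 4000 × 8/1230 = 26
- 4000 × 0.01 = 40
- At an assumed 3%: 4000 × 0.03 = 120

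These are upper values for the number miscoded, because women above the cutoff in step 1 are coded correctly.

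**Step 4. Effect on the overall proportion.** Let f be the share of all women with a known positive partner, L the fraction of them coded low risk, and q their PrEP uptake. If all of them should be on PrEP, the correct appropriate share among them is q and the coded share is L(1 − q) + (1 − L)q. The gap in the overall proportion is f·L·(2q − 1).

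- f = 1%, L = 1, q = 80% (assumed): 8 of 40 are coded appropriate when 32 of 40 are. (32 − 8)/4000 = 0.6 points.
- Same with L = 0.9: 26% coded appropriate against 80%, a gap of 0.54 points.
- f = 3% (assumed), L = 1, q = 80%: 0.03 × 0.6 = 1.8 points.
- q = 50%: no gap.

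**Step 5. Effect on the arm difference.** With L = 1, this group contributes f(qU − qT) to targeted minus universal as coded, and f(qT − qU) if coded correctly.

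- Equal uptake: both are zero.
- f = 1%, qU = 80%, qT = 50% (assumed): coded 0.01 × 0.3 = +0.3 points; correct −0.3 points.

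**Step 6. Newly found positive partners, only if risk is updated.** Protocol section 7 reports 16% scoring above 6 in the cohort behind the risk tool. If that tool is Table 5, the unknown-status share there is at most about 16%. Assuming 60% of those partners are tested and 10% of them are positive, 2000 × 0.16 × 0.6 × 0.10 = 19 targeted-arm women would drop by 6 points. With 40% tested and 5% positive it is 6; with 80% and 15% it is 38. Those with at least 7 lifetime partners, or reactive syphilis and at least 2, stay high risk.

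**The case against.** *The SAP does not name Table 5.* This is true. The aims speak of risk factors, Aim 1a in Protocol section 9 describes a score that takes in available self-test data, and the self-testing text mentions an algorithm that also uses refusal and fear of violence. The authors may therefore intend a positive result to count as high risk. But no rule in either document scores a positive result, and shell Table 2 points to the risk score. If another rule is meant, it still has to be written down.

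*Zero points may be justified.* Protocol section 7 reports that women in the Kenyan cohort who knew of a positive partner had lower HIV risk than the others, and suggests that their partners may be on ART or using condoms. Reported sustained partner suppression is also a listed reason to stop PrEP. This part stands: non-use can be right for some of these women. A reader might infer that the outcome is fully reversed for the whole group; the documents do not support that. Equally, the cohort finding does not make PrEP use inappropriate when the universal script advises it for any woman who knows her partner is positive.

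*Timing is partly answered.* Protocol Table 7 gives the PrEP counselling outcome form as the source, which points to the counselling decision. Those decisions recur over follow-up, so the visit remains open.

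*The effect is small.* This stands. A reader might also infer that reclassification after self-testing shifts the arm difference by several points in error. That is not supported. Most such reclassification would come from partners found negative, and the protocol treats a negative result as a real change in risk.

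**Conclusion.** The point holds as a coding fault in a defined subgroup. On the only score and cutoff the documents give, most women with a known HIV-positive partner are low risk, and the outcome then contradicts the protocol's own counselling advice. 'Most' rests on an assumed distribution of lifetime partners. The number whose partners are suppressed is not given, so I conclude that the coding is wrong for most of these women, not necessarily all.

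The size is about 26 to 40 of 4000 women and up to about 0.6 points in the overall proportion at an assumed 80% uptake. The arm comparison has no error at equal uptake, and about +0.3 instead of −0.3 points in the assumed 80% against 50% case. A reader might infer that the arm comparison is materially biased; nothing in the documents shows that uptake among these women will differ, and even the assumed case moves the difference little. The change is worth making because the outcome misclassifies a group the protocol itself advises to take PrEP, and because correcting it is cheap.

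**What to change.** In SAP section 2:

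- Define high risk for this outcome as a Table 5 score above 6 **or** a known HIV-positive partner.
- Classify from enrolment data, identically in both arms.
- Put no viral-suppression exemption in the main definition. Neither document shows suppression being collected at enrolment or for women not on PrEP.
- Add one sensitivity analysis with updated partner status: a positive partner is high risk, a negative result removes the 6 unknown-status points, and reported suppression is handled where it is recorded.

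In shell Table 2, report the four cells (high or low risk by PrEP yes or no) by arm, split by partner status positive, negative and unknown.

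The cost is a few lines of SAP text and some extra table rows. The main definition needs no new data: the risk score and partner status are collected from all women at enrolment, and Protocol Table 7 lists partner status as positive, negative or unknown. The downside is that enrolment classification does not credit the targeted arm for PrEP started, avoided or stopped after a self-test result. The sensitivity analysis is there to show that.
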